9.4 Sample Size and Power

This is a prospective, multicenter, randomized (2:1), unblinded study conducted in up to 2000 patients at risk of POAF based on the CHA2DS2-VASc and HASBLED scoring at up to 20 USA sites. All patients who undergo a valve or CABG (structural heart) procedure with direct visual access to the LAA will be eligible to participate based upon the inclusion and exclusion criteria defined in this protocol.

A total of up to 2000 patients (approx. 1333 in AtriClip group, approx. 667 in SOC group) at risk of POAF will be enrolled in this study. It is assumed that 40% of the patients will be diagnosed with POAF. A two treatment group one-sided Z-test with continuity correction and an $\alpha = 0.05$ will have 80% power to detect the difference between a medical management (SOC) safety rate of PS = 12.5% and a mechanical exclusion

Study Number: CP2015-2 CONFIDENTIAL Page 35 of 48

(AtriClip) safety rate of PC = 6.25% at 30-days post-op when the sample size (for completers) for patients diagnosed with POAF is 485 in the AtriClip group and 243 in the SOC group (a total sample size of 728). Adjusting for loss to follow-up, 533 patients in the AtriClip group and 267 in the SOC group (a total sample size of 800) are expected to be diagnosed with POAF.

9.5 Randomization

Upon enrollment, subjects will be assigned a sequential identification number at each site and a corresponding sealed envelope which will be opened prior to the index procedure to reveal the treatment group. Subjects will be randomized 2:1 (2 with AtriClip to 1 anticoagulation therapy and without AtriClip). Randomization sequences will be generated by AtriCure Statistician using SAS version 9.4 (SAS Institute Inc., Cary, North Carolina) and will be stratified by site.

9.6 Analysis Populations

Intent-To-Treat (ITT) Population: The effectiveness, safety, health economic and Qualify of life analyses will be based on the ITT population. The ITT Population is defined as all subjects randomized to either the AtriClip LAA Closure or anticoagulation therapy and without AtriClip LAA Closure group and on whom the surgical index procedure is attempted (even if the index procedure is aborted).

POAF Diagnosis (POAF) Population: This population will include all ITT subjects diagnosed with POAF. This will be the primary analysis population for effectiveness and health economic endpoints.

Per-Protocol (PP) Population: A PP population may be defined for effectiveness, health economic and Quality of Life analyses. This population is defined by POAF population but without any major protocol violations, that is, those that could potentially bias the results.

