9.2 Study Endpoints

The following endpoints will be collected for this hypothesis generating pilot study:

- 1. Perioperative complications associated with AtriClip placement. [Defined as: stroke, major bleeding that requires re-operation and/or transfusion of > 2 U packed red blood cells (PRBC) within any 24-hour period during the first 2 days' post-index procedure, myocardial infarction (MI), or death.]
- 2. Intraoperative successful exclusion of LAA. [Defined as no (0 mm) flow between LAA and LA and < 5 mm LAA remnant by intraoperative TEE with Doppler.]
- 3. Composite event rates between the group of subjects diagnosed with POAF (AtriClip vs no AtriClip) through 365 days' post index procedure and between the group of subjects not diagnosed with POAF (AtriClip vs no AtriClip) through 30 days' post index procedure. Events to be evaluated include: Thromboembolic & Hemorrhagic Events such as cerebrovascular accident (CVA), transient ischemic attack (TIA), peripheral ischemia, hemorrhagic stroke, neurologic bleed, gastrointestinal (GI) bleeds, or other major bleeding event.
- 4. Composite event (listed above) rates through 365-days post index procedure for all AtriClip patients, regardless of whether the patient develops POAF.
- 5. Healthcare resource utilization variance between groups as related to the composite events above. [Specifically hospital length-of-stay (LOS), reoperation for bleeding, neurologic consults for stroke or TIA, emergency department (ED) visits, and hospital readmissions.]

[figure not shown]

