9.7 Analysis of Study Endpoints

Study endpoints will be summarized by treatment group and overall as appropriate. Continuous variables will be summarized by presenting the number of subjects, mean, standard deviation, median, minimum, maximum by procedure group (AtriClip LAA Closure or anticoagulation therapy and without AtriClip LAA Closure). Tabulation of categorical variables by group will include counts and percentages. 95% confidence intervals will be provided as appropriate.

Since this is an exploratory study, additional analyses, additional analysis populations, covariates and summary tables and/or graphs will be generated as needed.

In all analyses described below, the null hypothesis will be a two-sided test of no treatment group difference. All statistical tests will use a two-sided significance level of α =0.05.

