9.7.2 Safety Analysis

A Pearson's Chi-Squared test will be used to compare the incidence of complications associates with LAA exclusion between the two procedure groups. Alternatively, a Fisher's Exact test will be used if justified by small cell counts (less than 5) and Clopper-Pearson (Exact) 95% CI will also be reported. Thromboembolic and hemorrhagic events will be similarly analyzed.

In addition, complications associated with LAA exclusion and thromboembolic/hemorrhagic might also be analyzed using multiple logistic regression model similar to the effectiveness endpoint (successful LAA exclusion) described above.

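### Sections 9.6 and 9.7.2 do not agree with Endpoint 3 and Section 9.4 on the population of the one powered comparison, and they make POAF subjects the primary set for an intraoperative outcome

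*Combined protocol and SAP*

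**What the plan says.** Four places bear on the population.

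- **Section 9.6, ITT paragraph:** "The effectiveness, safety, health economic and Qualify of life analyses will be based on the ITT population". ITT means randomised subjects in whom the index procedure was attempted.
- **Section 9.6, POAF paragraph:** the POAF set is the ITT subjects diagnosed with POAF. "This will be the primary analysis population for effectiveness and health economic endpoints". Safety is in the first list and absent from this one.
- **Section 9.7:** 9.7.1 (effectiveness and health economics) tests LAA exclusion and resource use. The composite's events appear only in 9.7.2 (Safety Analysis): "Thromboembolic and hemorrhagic events will be similarly analyzed". That section compares the two procedure groups and names no population.
- **Sections 9.2 and 9.4:** Endpoint 3 is worded "Composite event rates between the group of subjects diagnosed with POAF (AtriClip vs no AtriClip", through 365 days, with a separate comparison of no-POAF subjects through 30 days. Section 9.4 claims "80% power to detect the difference between a medical management (SOC) safety rate of PS = 12.5% and a mechanical exclusion" rate of 6.25% at 30 days, "when the sample size (for completers) for patients diagnosed with POAF is 485 in the AtriClip group" and 243 in the control group.

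Section 9.4 does not name the endpoint that it sizes. Endpoint 3 is the only clinical-event endpoint that compares the arms within POAF subjects, so I take it to be the one meant.

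**The concern.** Only Section 9.6 designates a primary population, and it does so by type of endpoint. The composite is labelled safety twice, in 9.4 and by its place in 9.7.2, so the POAF designation never reaches it. Endpoint 3 and the sample size assume that it does.

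The same labels misdirect LAA exclusion. It is assessed by intraoperative TEE, before postoperative AF can exist, and is the only clinical outcome in 9.7.1. Section 9.6 therefore makes its primary population the subjects who later develop POAF.

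Two things are at stake. The main comparison has two populations that could each be defended from the text, in an unblinded study where 9.7 allows further populations as needed and 9.8 foresees a detailed analysis plan only if needed. And the headline device-performance result would leave out most of the subjects who received the device.

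**Working it through.** **Inputs from Section 9.4.** Control rate 12.5%, AtriClip rate 6.25%, 2:1 allocation, one-sided 0.05, 80% power, continuity correction ("A two treatment group one-sided Z-test with continuity correction"); 485 + 243 = 728 POAF completers, 800 before losses; 40% POAF; 1333 and 667 subjects in total.

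**1. Reproduce the plan's figure.** With unpooled variance, control n before correction is

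n = (1.645 + 0.842)² × [0.125 × 0.875 + 0.0625 × 0.9375 / 2] / 0.0625² = 219.5.

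With d = 0.0625 and k = 2, the corrected value is n/4 × [1 + √(1 + 2(1 + 1/k)/(n·d))]² = 242.9, so 243. Power at 243 and 485 is

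Φ{[d − ½(1/243 + 1/485)] / SE − 1.645}, with SE = √(0.125 × 0.875/243 + 0.0625 × 0.9375/485) = 0.0239,

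which is Φ(0.842) = 80.0%. The stated size is reproduced, and it applies to POAF subjects only.

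**2. Retention.** 728/800 = 91%. Applied to all randomised subjects: 0.91 × 667 ≈ 607 control and 0.91 × 1333 ≈ 1213 AtriClip.

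**3. Illustrative pooled ITT comparison.** Assumptions not in the documents: the no-POAF event rate q is the same in both arms (no clip effect there), both strata are read at 30 days, and 91% complete. Then

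- control rate = 0.4 × 12.5% + 0.6q
- AtriClip rate = 0.4 × 6.25% + 0.6q
- difference = 0.4 × 6.25 = 2.5 points, whatever q is.

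The documents give no q, so a range is shown. The first power column uses the 9.4 method of step 1. The second uses the two-sided, uncorrected Pearson test of Section 9.7 ("All statistical tests will use a two-sided significance level of" 0.05).

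| Assumed q | Control | AtriClip | Power, 9.4 method | Power, 9.7 test |
|---|---|---|---|---|
| 0% | 5.0% | 2.5% | 77% | 78% |
| 1% | 5.6% | 3.1% | 73% | 72% |
| 2% | 6.2% | 3.7% | 68% | 66% |
| 4% | 7.4% | 4.9% | 61% | 58% |
| 6.25% | 8.75% | 6.25% | 55% | 50% |

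In the POAF set (243 and 485), the same two methods give 80.0% and 79.8%.

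**4. LAA exclusion.** Expected POAF subjects in the AtriClip arm: 0.4 × 1333 = 533. The POAF set therefore leaves out 1333 − 533 = 800 of 1333 AtriClip subjects, or 60%.

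**The case against.** A reader might infer that the plan orders the composite to be tested in all ITT subjects, and so puts the powered comparison in the wrong population. The documents do not support that.

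- Endpoint 3 is itself a written rule, repeated in the synopsis, Section 3.0 and Section 9.2. It fixes the comparison within POAF subjects and, separately, within no-POAF subjects. Objective 1 and Section 9.4 agree with it.
- The POAF set lies inside ITT, so analysing it can be squared with an ITT basis.
- No endpoint pools POAF and no-POAF subjects across arms. Endpoint 4 covers AtriClip subjects only.
- A pooled 365-day comparison would not fit the follow-up plan. Section 4.1 states 365-day follow-up for POAF subjects and for AtriClip subjects without POAF, with no matching statement for no-POAF control subjects.

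Nor does 9.6 reserve the POAF set for effectiveness and economics. ITT covers those too, and POAF is only the primary set for them. The study also calls itself a hypothesis-generating pilot, and with q = 0 the illustrated power loss is small (77% against 80%).

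All of this stands, and it limits the point to an inconsistency. It does not remove it. Endpoint 3 names two comparisons and makes neither primary, 9.7.2 names no population, and the one section that assigns primary populations omits safety. None of these arguments touches the LAA exclusion problem.

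**Conclusion.** The inconsistency is real and should be corrected. Sections 9.6 and 9.7.2 do not give the composite the population that Endpoint 3 and Section 9.4 assume, and they make a subset defined after surgery primary for an outcome fixed during surgery.

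The LAA exclusion part rests only on the 40% POAF assumption and leaves out about 60% of AtriClip subjects. The power figures for a pooled test, about 77% to 55% by the 9.4 method, show what the ambiguity could cost and do not describe an analysis that the plan clearly specifies. They depend on an assumed no-POAF rate of 0 to 6.25%, no clip effect in those subjects, an imposed 30-day window and 91% completion.

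Naming the POAF set as primary has its own limitation. POAF status arises after randomisation, in an unblinded study that monitors rhythm by local practice, so this is a post-randomisation subgroup comparison and should be described as one. The one-sided versus two-sided and 30-day versus 365-day differences between 9.4 and the rest of the plan are separate matters.

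**What to change.** In Section 9.6, with a cross-reference in 9.7.2, state that:

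- the POAF set is primary for the Endpoint 3 comparison sized in Section 9.4;
- the no-POAF comparison is separate, as Section 9.2 words it;
- any pooled ITT comparison of the composite is supportive and uses one common window;
- the POAF comparison is a post-randomisation subgroup and will be interpreted as such;
- LAA exclusion is reported in all AtriClip-arm subjects in whom placement was attempted, not in the POAF subset. Section 5.2.1 leaves the appendage intact in the other arm.

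Leave the populations for Endpoints 1 and 5 as Section 9.6 has them; nothing here justifies moving them.

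The cost is a few lines of text. The required 485 and 243 POAF completers, the data collected and the conduct of the study do not change.

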9.7 Analysis of Study Endpoints

Study endpoints will be summarized by treatment group and overall as appropriate. Continuous variables will be summarized by presenting the number of subjects, mean, standard deviation, median, minimum, maximum by procedure group (AtriClip LAA Closure or anticoagulation therapy and without AtriClip LAA Closure). Tabulation of categorical variables by group will include counts and percentages. 95% confidence intervals will be provided as appropriate.

Since this is an exploratory study, additional analyses, additional analysis populations, covariates and summary tables and/or graphs will be generated as needed.

In all analyses described below, the null hypothesis will be a two-sided test of no treatment group difference. All statistical tests will use a two-sided significance level of α =0.05.

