1.0 INTRODUCTION

The traditional standard of care for patients with POAF is oral anticoagulation (OAC) therapy as prophylaxis of thromboembolic events. Recent clinical literature from Gallego et al (Gallego, Relation of the HAS-BLED bleeding risk score to major bleeding, cardiovascular events, and mortatlity in anticoagulated patients with atrial fibrillation., 2012) suggests that the risk of major bleeding exceeds the risk of thromboembolic events in AF patients at a HAS-BLED score of > 3. Gallego et al. also reported that patients with low CHADS score (e.g., 0 – 1) have lower major bleeding risk than those patients with CHADS >=2. Although Gallego et al. focused on HAS-BLED > 3, the study recruited 800 (83%) and 740 (77%) patients with HASBLED>=2 and CHADS>=2, respectively. In fact, 472 (49%) of the patients recruited in the study had a HASBLED score of 2. Other peer-reviewed research from Tung et al (Tung, 2015) identifies that the highest risk for major bleeding occurs within the first 30 days of initiating OACs. Therefore, this study focuses entirely on a subset of patients that are vulnerable to both initiation of OACs as well overalls risks of OAC therapy.

Literature and current practice reinforce the fact that this subset of high risk AF patients are not routinely being started on OACs. In a recent meta-analysis from Lip et al (Lip, Underuse of Oral Anticoagulation in AF, A systematic review, 2010), looking at high risk patients (defined as those with a CHADS > 2) only 39% of AF patients in the U.S. were on OAC therapy.

This study intends to monitor a subset of patients with specific risk factors where both the risk of thromboembolic events and major bleeding intersect resulting in significant clinical equipoise both in literature and in current "real life" clinical practice.

Use of the AtriClip device may eliminate the nidus for AF-related thrombi originating in the Left Atrial Appendage. While not the focus of this study it is believed that this may contribute favorably to the primary composite endpoint of major bleeding, stroke and TIA. This research may begin to better inform clinical practice for those treating these high risk patients and continue to ascertain the risk of major bleeding vis-

Study Number: CP2015-2 **CONFIDENTIAL** Page 13 of 48

à-vis the risk of thromboembolic events in AF patients at a HAS-BLED score >=2.

Need for Treatment in ATLAS

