9.7.1 Effectiveness and Health Economic Analysis

A Pearson's Chi-Squared test will be used to compare the incidence of successful LAA exclusion between the two procedure groups. Alternatively, a Fisher's Exact test will be used if justified by small cell counts (less than 5) and Clopper-Pearson (Exact) 95% CI will also be reported.

In addition, LAA exclusion might also be analyzed using multiple logistic regression model with the proportion of the event of successful LAA exclusion as the dependent variable and the following independent variables: sites (or clusters of sites), surgical approach (sternotomy, right mini-thoracotomy or other), age, gender, CHA2DS2- VASc score, HASBLED score and relevant interaction terms.

Study Number: CP2015-2 CONFIDENTIAL Page 36 of 48

Healthcare resource use will be assessed by examining either total resource use, treatment costs or formal cost effectiveness/cost utility analysis. Resource use such as hospital length of stay, OR time, and total treatment costs will be compared between the treatment groups using a two-way analysis of variance (ANOVA) model with procedure group (AtriClip LAA Closure or anticoagulation therapy and without AtriClip LAA Closure) and site as fixed effects in the model.

These endpoints will also be compared using the two-sided t-test. A Shapiro-Wilk test of normality will be performed and if the normality assumption is not met, an approximate non-parametric model (e.g. Wilcoxon rank-sum test) may be performed.

A Pearson's Chi-Squared test will be used to compare difference in 30 day readmits, number of neurological consults, additional procedures, and patient medication use between the two procedure groups.

Formal economic models utilizing treatment effectiveness (Quality adjusted life years, costs to reduce stroke, etc.) may be built with collected data and other secondary sources accounting for specific country perspective and discounted appropriately.

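### No endpoint is ranked and every test is run at two-sided 0.05, so the plan names no main comparison against which a chance significant result could be judged

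*Combined protocol and SAP*

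**What the plan says.** Section 9.2 opens with "The following endpoints will be collected for this hypothesis generating pilot study" and lists five numbered endpoints, as section 3.0 does. None is called primary or secondary. Section 9.7 calls the study exploratory, allows further analyses and populations as needed, and sets one rule for all tests: "All statistical tests will use a two-sided significance level of α =0.05". No testing order, multiplicity rule or limit on interpreting p-values is given.

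Other sections write as if a main result exists:

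- The Introduction (1.0) refers to the "primary composite endpoint of major bleeding, stroke and TIA".
- Section 9.4 sizes one comparison, in patients with POAF at 30 days, using "A two treatment group one-sided Z-test with continuity correction" at 0.05. It gives "485 in the AtriClip group and 243 in the SOC group (a total sample size of 728" as the number of completers needed.
- Section 9.6 makes the POAF population primary for effectiveness and health economic endpoints.

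The comparisons themselves are in 9.7.1 and 9.7.2. For example, a chi-squared test is to "compare difference in 30 day readmits, number of neurological consults, additional procedures, and patient medication use between the two procedure groups".

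**The concern.** A reader of the final report needs to know which comparison the trial was built to answer. The plan does not settle this, because the places that hint at it disagree:

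- **Components.** The composite in the Introduction has three components. Endpoint 3 is wider, adding peripheral ischemia, gastrointestinal bleeds and other events, and its list is introduced as examples.
- **Time point.** Section 9.4 sizes a 30-day rate. Endpoint 3 follows POAF subjects to 365 days.
- **Endpoint.** Section 9.4 speaks only of a safety rate and does not tie it to any numbered endpoint.
- **Sidedness.** Section 9.4 is one-sided; section 9.7 is two-sided.

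Without a named main comparison, any result that crosses 0.05 has the same standing in the plan as the one that justified the sample size. The study is unblinded, section 12.1 anticipates no independent oversight, and section 9.8 provides for a detailed analysis plan only if needed. No later document is therefore guaranteed to close the gap.

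**Working it through.** **1. Reproducing the plan's sample size.** Inputs from section 9.4: control rate 12.5%, AtriClip rate 6.25%, difference d = 0.0625, 2:1 allocation, one-sided 0.05, 80% power, continuity correction. With unpooled variance, the control-arm size is

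n = (1.645 + 0.842)² × (0.125×0.875 + 0.0625×0.9375/2) / 0.0625² = 219.5.

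With the Fleiss correction, n′ = (n/4) × [1 + √(1 + 3/(n·d))]² = 242.9, rounded to 243. Section 9.4 states 243 and 485, so its figure is reproduced.

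**2. The same formula at the two-sided level of section 9.7.** With 243 and 485 completers:

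- Standard error = √(0.109375/243 + 0.058594/485) = 0.02389.
- Correction = ½(1/243 + 1/485) = 0.00309.
- (0.0625 − 0.00309)/0.02389 = 2.486.
- One-sided: Φ(2.486 − 1.645) = 0.80.
- Two-sided: Φ(2.486 − 1.960) = 0.70.

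Other two-sided variants give 0.76 (pooled, corrected) and 0.80 (pooled, uncorrected). Reaching 80% two-sided by the method of 9.4 needs about 303 + 606 = 909 completers, against 728.

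**3. Counting the between-arm comparisons.** Endpoint 4 covers AtriClip patients only, so it has no between-arm test. LAA exclusion is set aside because section 5.2.1 leaves the control appendage intact, so no difference is not a realistic hypothesis there. What remains in 9.7.1 and 9.7.2:

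- continuous resource use: length of stay, OR time, total cost (3)
- categorical resource use: 30-day readmission, neurological consults, additional procedures, medication use (4)
- complications (1)
- the composite, in POAF and in non-POAF subjects as endpoint 3 divides it (2)

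That makes ten. A stricter count removes three. OR time goes because placing a clip takes some time. Total cost goes because 9.3 says only that costs may be assigned. The composite counts once because 9.7.2 does not say that it is tested twice. That leaves seven. Neither count includes the duplicate t-tests or Wilcoxon tests, the optional logistic models or the optional per-protocol set.

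**4. Chance of at least one p<0.05 with no true effect.** For k independent tests this is 1 − 0.95^k.

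| k | chance |
|---|---|
| 7 | 30.2% |
| 8 | 33.7% |
| 9 | 37.0% |
| 10 | 40.1% |

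The documents give no correlations. Simulating ten equally correlated normal test statistics (300,000 draws) gives about 35%, 29% and 21% at assumed correlations of 0.3, 0.5 and 0.7. The chance of at least one false positive favouring AtriClip is 1 − 0.975^10 = 22.4% for ten independent tests.

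**The case against.** The strongest reply is that the study is labelled a pilot, hypothesis generating and exploratory, and states no success criterion. On that footing formal multiplicity control is not required, and section 9.7 already offers 95% confidence intervals as appropriate. This stands: the absence of an adjustment is not in itself an error. It does not explain why every comparison carries a significance level, or why up to 2000 patients are justified by a power statement for a comparison that the endpoint list does not single out.

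A second reply is that the main comparison can be inferred: objective 1, the sizing in 9.4 and the primary population in 9.6 all point to AtriClip versus no AtriClip in POAF subjects. This stands for the population and the contrast, but not for the components, time point or sidedness.

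Four stronger readings are tempting but unsupported:

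- **That a false positive is more likely than not.** The figures are 21–40%. With independent tests, one half is passed only at 14 (51.2%).
- **That all five endpoints are tested between arms.** Endpoint 4 is single-arm.
- **That repeating the tests in the ITT, POAF and per-protocol sets multiplies the risk.** The sets are nested, so the tests would be highly correlated, and the per-protocol set is optional.
- **That the trial is plainly underpowered.** The 70% belongs to the corrected, unpooled formula of 9.4. Section 9.7.2 plans a Pearson chi-squared test; if uncorrected, its approximate two-sided power on the same rates is 80%. The defect is that 9.4 and 9.7 describe different tests.

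**Conclusion.** The point holds in a limited form. The plan attaches two-sided 0.05 to about seven to ten between-arm comparisons besides LAA exclusion and names none as primary, while three other sections assume that a main result exists. The risk of at least one chance finding is substantial, four to eight times the nominal 5% (21% to 40%). The upper figures assume independence; the lower ones rest on correlations that are assumptions. All figures suppose no true effect on any counted outcome.

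The power figure rests on the plan's own 30-day rates. If 365 days is chosen as the time point, the documents give no rates from which to compute power. The matter should be corrected because it decides what the trial can claim. It does not invalidate the design.

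**What to change.** - **Section 9.2:** name one primary comparison, the thromboembolic/hemorrhagic composite, AtriClip versus no AtriClip, in POAF subjects. Give one closed component list, reconciling the Introduction with endpoint 3, and one time point, reconciling 30 days in 9.4 with 365 days in endpoint 3. Use the same endpoint name in 1.0 and 9.4.
- **Sections 9.4 and 9.7:** make the sidedness and the test agree. If two-sided 0.05 is kept, restate the power in 9.4 as about 70% for 485 and 243 completers by its present method and assumed rates. If a different test is named, recompute the power for that test. If 365 days is chosen, state the assumed rates at that time point.
- **Section 9.7:** replace the sentence that applies 0.05 to all tests. Only the primary comparison is tested at that level. All others are reported as estimated differences with 95% confidence intervals, and any p-values are descriptive.

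This costs a few sentences and needs no additional patients or data. The downsides are that secondary results can no longer be called significant and the stated power looks less favourable. A Bonferroni correction over ten tests (0.005 each) would cost more: power for the sized comparison would fall to about 0.37 (unpooled, corrected) to 0.53 (pooled, uncorrected).
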